3.3.6 Study Drug Exposure and Compliance

Days of exposure to study drug will be calculated as date of last dose of study drug as recorded on the end of study form – date of first dose of study drug + 1. Note that the exposure calculation is intended to describe the length of time a subject was exposed to study drug and therefore does not take study drug interruptions into account. Days of exposure to study drug will be summarized based on the Safety Analysis Set with descriptive statistics and with counts and percentages of subjects with exposure in the following categories:

- <4 weeks (<29 days)
- 4 to <8 weeks (29 – 56 days)
- 8 to <12 weeks (57 – 84 days)
- 12 to <16 weeks (85 – 112 days)
- 16 to <20 weeks (113 – 140 days)
- 20 to <24 weeks (141 – 168 days)
- ≥24 weeks (≥169 days)

Percent compliance to the study drug regimen will be calculated as $100 \times \text{number of actual capsules taken} / \text{number of expected capsules taken}$. The number of actual capsules taken will be calculated as number of capsules dispensed – number of capsules returned. If study drug is not returned, the number of capsules returned will be considered 0 for the compliance calculation, i.e. it will be assumed that the subject took all capsules. The number of capsules expected will be calculated as $2 \times \text{days of exposure}$. Percent compliance to the study drug regimen will be summarized based on the Safety Analysis Set with descriptive statistics and with counts and percentages of subjects with compliance in the following categories:

- <80%
- 80-120%
- >120%

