3.1. Study Design

This is a phase 2 proof of concept study to evaluate the efficacy and safety of open-label NTZ 500mg bid in a NASH population with NASH induced Stage 2 or 3 fibrosis.

The study will include a screening visit within 6 weeks of randomization (Day 1) followed by a 24-week treatment period consisting of daily, BID, oral administration of NTZ and an end of treatment follow up period of 4 weeks.

Patients will come to the research center and complete the following visits:

- Screening Visit within 6 weeks of Randomization
- Day -14 Deuterated Water Run-In
 - Day-14, Day-11, Day-7 and Day 1: sampling for labelling of Deuterated water during run-in
- Repeat baseline labs for ALT, AST, total bilirubin, ALP, CPK collected at least 4 weeks from initial screening.
- Day 1 Randomization: start of treatment
- Every 4 weeks after randomization until 20 weeks post randomization

- 22 weeks post randomization and Deuterated Water Administration Period:
 - 22 weeks plus 3 days
 - sampling for labelling of Deuterated water on Day 155, 158, 162, and Day 169/24 weeks post randomization: End of Treatment
- 4 Week Post Treatment Follow Up

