3.2. Treatment Plan and Regimen

NTZ will be administered in an open label fashion to participating subjects as 500mg bid, for 24 weeks.

4. Subject Population

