5.5. Dosage and Administration

Patients will be instructed to take one tablet of 500mg NTZ mg orally, twice a day with water during a meal, approximately 12 hours apart.

The study staff will administer the first dose of the medication at the research center. Patients will self-administer the evening dose on Day 1 and twice a day thereafter, when not attending

a visit at the research center. On scheduled follow up visit days while the patient is being treated with study drug, the patient will be directed to bring back all used and unused study medication containers. Compliance will be checked by the Investigator or designee during those visits and registered in the electronic Case Report Form (eCRF).

If treatment is interrupted, whatever the cause, duration and reason of the interruption will be documented.

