3 STATISTICAL METHODOLOGY

3.1 General Considerations

3.1.1 Analysis Day

Analysis day will be calculated from the date of first dose of study drug. The day of the first dose of study drug will be Day 1, and the day immediately before Day 1 will be Day -1. There will be no Day 0.

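### SAP 3.3.6 counts exposure inclusively, so 24 weeks is 168 days, yet 168 days is tabulated as under 24 weeks and the 24-week row starts at 169

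*SAP*

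**What the plan says.** SAP 3.3.6 takes the date of last dose from the end of study form and subtracts the "date of first dose of study drug + 1". It states that this measures the span of exposure and ignores interruptions. The result is summarised as a continuous variable and in seven categories on the Safety Analysis Set. The last two categories are "20 to <24 weeks (141 – 168 days" and "≥24 weeks (≥169 days".

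The same section uses the day count for compliance: "The number of capsules expected will be calculated as" twice the days of exposure.

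SAP 3.1.1 fixes the numbering: "The day of the first dose of study drug will be Day 1", with no Day 0. Protocol 3.2 gives the regimen: "NTZ will be administered in an open label fashion to participating subjects as 500mg bid, for 24 weeks". Under Protocol 5.5 the first dose is given at the center on Day 1, and "Patients will self-administer the evening dose on Day 1 and twice a day thereafter". Protocol 3.1 places the last treatment-period visit at "Day 169/24 weeks post randomization: End of Treatment".

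**The concern.** Each category carries two definitions, a week label and a day range. Under the SAP's own formula they disagree at every boundary. A subject dosed from Day 1 through Day 168 has exactly 24 weeks of exposure but is reported as having less.

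The primary objective is safety and tolerability after 24 weeks of treatment. The top row of this table is where a reader looks to see how many subjects had treatment spanning that period. If completers typically take their last dose the day before the Day 169 visit, the row could show few or none of them.

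**Working it through.** **Inputs**

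- Exposure = last-dose date − first-dose date + 1 (SAP 3.3.6)
- First dose is on Day 1, with no Day 0 (SAP 3.1.1)
- Planned treatment is 24 weeks, twice daily (Protocol 3.2), with both doses starting on Day 1 (Protocol 5.5)
- Visit days for Weeks 4, 8, 12, 16, 20 and 24 are 29, 57, 85, 113, 141 and 169 (Protocol Table 1)
- Planned enrolment is 20 (Protocol 4.1)

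**1. Where the printed bounds come from.** Day 1 plus 28, 56, 84, 112, 140 and 168 days gives 29, 57, 85, 113, 141 and 169. These are the SAP's lower bounds and also the visit days. Day 169 is therefore right as the date that falls 24 weeks after Day 1.

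**2. What the formula returns.** If the last dose is on study Day d, exposure = (d − 1) + 1 = d days.

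| Last dose | Exposure (days) | Weeks = days/7 | SAP row | Row by week label |
|---|---|---|---|---|
| Day 167 | 167 | 23.86 | 20 to <24 | 20 to <24 |
| Day 168 | 168 | 24.00 | 20 to <24 | ≥24 |
| Day 169 | 169 | 24.14 | ≥24 | ≥24 |

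**3. The other boundaries.**

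| Exposure (days) | Weeks | SAP row | Row by week label |
|---|---|---|---|
| 28 | 4.0 | <4 | 4 to <8 |
| 56 | 8.0 | 4 to <8 | 8 to <12 |
| 84 | 12.0 | 8 to <12 | 12 to <16 |
| 112 | 16.0 | 12 to <16 | 16 to <20 |
| 140 | 20.0 | 16 to <20 | 20 to <24 |

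Comparing range with label for every count from 1 to 199 days gives disagreement at 28, 56, 84, 112, 140 and 168 only.

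**4. Cross-check against the dosing count.** Twenty-four weeks of twice-daily dosing is 24 × 14 = 336 doses. The compliance formula expects 2 × 168 = 336 at 168 days and 2 × 169 = 338 at 169 days, which is two more than 24 weeks. Since both doses begin on Day 1, the 336th dose falls on Day 168 if none is missed.

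**5. Effect on the table.** If m of 20 subjects have their last dose on Day 168, the top row is low by m/20 = 5m percentage points: 5 for m = 1, 50 for m = 10 and 100 for m = 20 (0/20 shown instead of 20/20).

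**The case against.** The ranges are contiguous and do not overlap, so each subject falls in exactly one row, and a reader who sees the day bounds can tell what the top row means. The cuts follow the protocol's calendar, and as elapsed time from first dose the labels are right: Day 169 is 168 days after Day 1 and Day 168 only 167. Harm requires a last dose on exactly a boundary day, which no section states. Supply does not force a Day 168 stop, since a four-week box holds 6 × 12 = 72 tablets against 56 needed. The row shows a first-to-last-dose span that ignores interruptions, so it never proved that 24 weeks of drug were taken. Completion and early discontinuation are reported separately.

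Much of this stands, and it limits the consequence. The compliance cross-check confirms the arithmetic but does not show a second error, because compliance uses the day count and never the categories.

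The calendar reading explains the cuts but does not reconcile them with the formula. The SAP applies the ranges to an inclusive count and nowhere describes them as study days. Dropping the +1 while keeping the ranges would not help either: a last dose on Day 169 would then give 168 days, which would still fall in the 141–168 row.

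A last dose on Day 168 is also plausible. Protocol 6.4 lists an in-clinic dose on Day 1 and at Weeks 4, 8, 12, 16 and 20, but none at the Week 24 visit, and Table 1 shows no dispensing there. A subject seen on Day 169 whose last dose was the day before has exactly 168 days.

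**Conclusion.** The error is certain as arithmetic: under the SAP's formula, label and day range disagree by one day at each of the six boundaries, and exactly 24 weeks is classed as less than 24.

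Its effect on the reported table cannot be fixed from the documents. It is 5 percentage points per subject with a last dose on Day 168, assuming 20 subjects in the Safety Analysis Set, with bounds of 0 (no such subject) and 100 (all 20). Subjects who also dose on Day 169 are classed correctly.

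The importance is small. The table is descriptive, raw days of exposure are summarised in the same section, the compliance calculation is untouched, and no test or analysis set depends on the categories. It should still be corrected, because following the SAP as written could report full-course subjects as short of 24 weeks.

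**What to change.** In SAP 3.3.6, keep the exposure formula and the week labels and replace the day bounds:

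| Label | Days |
|---|---|
| <4 weeks | <28 |
| 4 to <8 weeks | 28–55 |
| 8 to <12 weeks | 56–83 |
| 12 to <16 weeks | 84–111 |
| 16 to <20 weeks | 112–139 |
| 20 to <24 weeks | 140–167 |
| ≥24 weeks | ≥168 |

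If the team did intend visit-day cuts, the rows should be labelled as study day of last dose and not as weeks of exposure.

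The cost is one SAP edit and one programming specification before database lock. No data collection, analysis set or test changes.

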6.6.3. Dose Adjustment

Enrolled subjects who experience treatment emergent adverse events should be monitored closely and may have the NTZ dose adjusted at the Principal Investigator's discretion.

Enrolled subjects who experience a possible treatment emergent adverse event will be assessed for symptoms and further biochemical assessments as follows:

- GI Adverse Events: the subject will be assessed for abdominal pain, loss of appetite, nausea and vomiting. Blood will be collected for amylase and lipase assessment to rule out pancreatitis.
- Kidney Function Adverse Events: the subject will have blood samples collected for eGFR to rule out kidney dysfunction.
- Musculoskeletal Adverse Events: the subject will be assessed for fatigue, muscle aches and pain. Blood samples will be collected for Creatine Kinase.

The following procedure will be followed for dose adjustments:

1. Patients will be asked to hold drug for 3 days
2. After the 3-day drug hold, patients will be reassessed for adverse event symptoms.
 - If the AE symptoms have resolved following 3 days of drug hold, the patient will discontinue NTZ dosing permanently and will be followed per the schedule of assessments.

If the AE symptoms have not resolved following 3 days of drug hold, the patient will be restarted on a reduced dose of 500 mg NTZ, once a day for 7 days. Patients will be evaluated for treatment emergent adverse events and consideration for resuming the dosage of 500mg NTZ twice a day. PI may determine that the patient should remain at the 500 mg NTZ once a day dose following 7 days of reduced dose. In such scenarios, the patient will be monitored and consideration for resuming the dosage of 500 mg NTZ twice daily will be evaluated at each subsequent visit.

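### SAP 3.3.6 expects two tablets on every day from first to last dose, so compliance is understated for patients who restart after a protocol-directed hold or once-daily period

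*SAP*

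**What the plan says.** SAP 3.3.6 builds percent compliance in three steps.

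- **Exposure.** "Days of exposure to study drug will be calculated as date of last dose of study drug as recorded on the end of study form" minus the first-dose date, plus 1. The SAP adds that this figure "does not take study drug interruptions into account".
- **Denominator.** "The number of capsules expected will be calculated as" 2 × days of exposure.
- **Numerator.** "The number of actual capsules taken will be calculated as number of capsules dispensed – number of capsules returned". For drug that does not come back, "it will be assumed that the subject took all capsules".

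The result is summarised with descriptive statistics and in three categories: below 80%, 80-120% and above 120%.

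The protocol departs from two tablets a day in several places. Section 6.6.3 asks for a 3-day hold and, for patients who then restart, one tablet a day for 7 days. After that, "PI may determine that the patient should remain at the 500 mg NTZ once a day dose following 7 days of reduced dose", with a return to twice daily considered at each later visit and no maximum duration stated. Sections 6.6.1 and 6.6.4 require interruption for Grade IV events or liver criteria, with restart possible after review by the Data Safety Monitoring Board (DSMB). On records, section 5.5 says: "If treatment is interrupted, whatever the cause, duration and reason of the interruption will be documented".

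**The concern.** Ignoring interruptions is reasonable for describing how long a patient was on study. It is not reasonable to carry the same day count into the denominator of a measure of adherence to the regimen, because the protocol itself changes the regimen. On a directed hold day the patient is told to take no tablets, and on a once-daily day one tablet, yet the SAP expects two on both.

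What is at stake is how one descriptive table reads. The primary objective is safety and tolerability of 500 mg twice daily in 20 subjects. Patients who could not stay on twice-daily dosing bear on that objective; patients who forgot tablets are a different matter. The planned summary can put both in the same row. With 20 treated subjects, each one placed there moves the row by 1/20 = 5 percentage points.

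**Working it through.** The documents give no compliance figure to reproduce, so the check applies the SAP formula to regimens that the protocol allows.

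**Inputs**
- D = days of exposure. The planned value is 24 weeks = 168 days (Protocol 5), so 2 × 168 = 336 expected tablets.
- h = directed hold days, inside the first-to-last-dose window.
- q = once-daily days.
- Assumed: perfect adherence to instructions and return of every unused tablet.

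**Formula**

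Tablets taken = 2(D − h − q) + q. SAP compliance = 100 × taken / 2D = 100 × [1 − (2h + q)/2D]. It falls below 80% when 2h + q > 0.4D. At D = 168 that means 2h + q > 67.2.

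**Results**

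| Directed regimen | Taken / expected | SAP compliance |
|---|---|---|
| One cycle: 3-day hold, 7 once-daily days, D = 168 | 323/336 | 96.1% |
| Five cycles, D = 168 | 271/336 | 80.7% |
| Six cycles, D = 168 | 258/336 | 76.8% |
| 3-day hold, 61 once-daily days, D = 168 | 269/336 | 80.1% |
| 3-day hold, 62 once-daily days, D = 168 | 268/336 | 79.8% |
| 33-day interruption, D = 168 | 270/336 | 80.4% |
| 34-day interruption, D = 168 | 268/336 | 79.8% |
| One cycle, D = 33 | 53/66 | 80.3% |
| One cycle, D = 32 | 51/64 | 79.7% |
| Hold Days 29-31, then once daily Days 32-168 | 193/336 | 57.4% |

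In the last row, tablets taken are 28 × 2 + 3 × 0 + 137 × 1 = 193.

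**Sensitivity to D.** At D = 169, 62 once-daily days after a 3-day hold, or a 34-day interruption, gives 270/338 = 79.9%. At D = 170 either gives 272/340 = 80.0% exactly, inside the middle category. The thresholds are therefore approximate.

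**Permanent stops.** If the patient never restarts after the hold, the last dose precedes the hold. The hold then lies outside the exposure window and does not affect the score.

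**Opposite bias.** Protocol 5.2 supplies 6 × 12 = 72 tablets per 4-week box, against 56 needed for 28 days. A patient who returns nothing from six boxes scores 432/336 = 128.6%. This is a separate error and does not correct the one above.

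**After the change.** With expected tablets taken from the prescribed regimen, the single-cycle patient has 323 expected and 323 taken, or 100%. The same holds in every row of the table.

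**The case against.** The best reply is that very little turns on this. A reader might infer that patients who follow instructions are generally reported as non-compliant. The documents do not support that: the SAP gives no category that label, the standard single cycle scores 96.1%, and falling below 80% takes a long reduction, a long interruption, repeated cycles or a short exposure. The 57.4% case needs 137 consecutive once-daily days although return to twice daily is reconsidered at each visit. It shows what is permitted, not what is likely.

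A reader might also infer that trial conclusions are affected or that the two kinds of patient cannot be told apart. Neither follows. Tolerability is assessed from adverse events, laboratory tests, vital signs, ECGs and examinations (Protocol 8.5, SAP 2.1). The fractional synthesis rate is analysed in the Full Analysis Set, and no analysis set or test uses compliance. Interruptions are documented (Protocol 5.5), the adverse event record has a temporary-withdrawal action (Protocol 7.2.3), and SAP 7 lists all available data. With 20 subjects, each low score can be looked up.

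Finally, the lack of a dose-intensity measure could be called a gap: a patient who stops on Day 30 after 60 tablets scores 60/60 = 100%. But the exposure categories in SAP 3.3.6 and the disposition table in SAP 3.3.1 largely show early stopping, so that table is an optional extra.

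All of this limits the consequence. None of it repairs the denominator, and no other section adjusts expected tablets for directed holds or reductions.

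**Conclusion.** The point holds in a limited form. As written, the formula understates compliance for any adherent patient who restarts after a directed hold or reduction. The shortfall is 100 × (2h + q)/2D percentage points: 3.9 for one standard cycle over 168 days, and more than 20 for the prolonged cases above. The below-80% row of the summary can therefore mix missed tablets with directed reductions, while listings can still separate them. No efficacy or safety estimate changes.

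The figures assume exact adherence, full return of unused tablets and, unless stated otherwise, 168 days of exposure. How many patients are affected cannot be derived from the documents. They set no maximum for once-daily dosing and no time limit for the DSMB's causality assessment; the only review frequency stated is every 3 months (Protocol 6.6.5, SAP 4).

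The correction is worth making because it is specific and cheap, and because it concerns a reported figure in a small tolerability study.

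**What to change.** In SAP 3.3.6, define expected tablets as the sum over days from first to last dose of the number prescribed that day: 0 on directed hold days, 1 on once-daily days and 2 otherwise. Apply the 80% and 120% cut-offs to that measure. Leave days of exposure as it is, and add a count of patients with any directed hold or reduction. Replace capsules with tablets, since the product is a tablet (SAP 2.2.3).

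The cost is one extra derivation and a check on data capture. Protocol 5.5 covers interruptions, not reductions. Protocol 9.6 requires start and end dates with the dose regimen in source records, which is not the same as the eCRF. The action-taken list in Protocol 7.2.3 has no entry for a reduced dose. The sponsor should confirm that dose-reduction dates reach the eCRF.

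The sponsor should also confirm the two branches of Protocol 6.6.3. As printed, symptoms that resolve on the hold lead to permanent discontinuation and symptoms that persist lead to restart, whereas 6.6.1 makes resolution or return to baseline a condition of restart. The passages must be reconciled, because they decide which patients have a hold inside the exposure window.

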3.4 Efficacy Assessments

3.4.1 Fractional Synthesis Rate

FSR of circulating plasma proteins will be measured at baseline and after 24 weeks of treatment. The observed change and percent change in FSR from baseline to Visit 10 Week 24 between the first and second deuterated water loading periods will be assessed to determine the effects of NTZ 500 mg BID on de novo collagen synthesis in the Full Analysis Set.

Wilcoxon signed-rank test will be used for statistical inference. Summary statistics of change in FSR (observed change and percent change) from baseline in FSR will be reported and evaluated at a significance level of 0.05. The p-value from Wilcoxon signed rank test will be reported. Only subjects with FSR at both baseline and Visit 10 Week 24 will be included in analysis. Liver Stiffness

FibroScan

Summary statistics for liver stiffness as measured by FibroScan will be provided at baseline and Visit 10 Week 24/Early Termination, including the change from baseline, based on the Full Analysis Set.

Student's T-test will be used for statistical inference. Summary statistics of change in liver stiffness as measured by FibroScan from baseline in FSR will be reported and evaluated at a significance level of 0.05. The 95% confidence interval (CI) and p-value from Student's T-test will be reported. Only subjects with FibroScan at both baseline and Visit 10 Week 24/Early Termination will be included in analysis.

MRE

Summary statistics for liver stiffness as measured by MRE will be provided at baseline, Visit 4 Week 12, and Visit 10 Week 24/Early Termination, including the changes from baseline, based on the Full Analysis Set. Student's T-test will be used for statistical inference in the same manner as for FibroScan.

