8.1.2. Secondary Endpoints

The secondary endpoints are:

- To assess the % change in FSR from baseline to end of treatment (24 weeks of treatment)
- To assess the change in liver stiffness by MRE from baseline to 12 weeks and 24 weeks of treatment
- To assess the change in liver stiffness by fibroscan from baseline to 24 weeks of treatment
- To assess the change from baseline to 12 weeks and 24 weeks of treatment of fibrosis serum biomarkers and scores

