8.3. Data Handling Conventions

Continuous variables will be summarized with descriptive statistics (i.e., sample size, mean, standard deviation, minimum, maximum, median, and quintiles). Categorical variables will be summarized with descriptive statistics (i.e., sample size, frequency counts, and percentage). Statistical testing on change from baseline values will be performed using analysis of variance techniques with a term for baseline in the model. Statistical significance will be considered to have been reached at an alpha level of 0.05.

Baseline value is measured on Day 1 of the treatment period before the administration of NTZ.

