8.6. Secondary Efficacy Analyses

8.6.1. FSR

Fractional Synthesis Rate of circulating plasma proteins will be measured at Baseline, and after 24 weeks of treatment.

The change in FSR (absolute and relative) from baseline to end of treatment between the first and second deuterated water loading periods will be assessed to determine the effects of NTZ 500mg BID on de novo collagen synthesis in the Full Analysis Set.

Wilcoxon signed-rank test will be used for statistical inference. Estimated mean, standard error and 95% confidence interval of change in FSR (absolute and relative) change from baseline in FSR will be reported and evaluated at a significance level of 0.05. Exploratory analyses may also be performed to evaluate the association of individual exploratory biomarkers or combination of biomarkers with clinical measurements and other risk factors.

Additional details will be provided in the SAP.

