2 STUDY OVERVIEW

2.1 Study Objectives and Endpoints

Primary	
Objective	Endpoint
To evaluate the safety and tolerability of NTZ 500 mg twice daily (BID) after 24 weeks of treatment in patients with non alcoholic steatohepatitis (NASH)-induced stage 2 or stage 3 fibrosis.	Adverse events (AEs) including treatment-emergent AEs (TEAEs) and serious AEs (SAEs), laboratory evaluations, vital signs, electrocardiograms (ECGs), and physical examinations.
Secondary	
Objective	Endpoint
To determine the effect of oral administration of NTZ 500 mg BID on de novo collagen synthesis through Fractional Synthesis Rate (FSR) of circulating plasma proteins in patients with NASH induced stage 2 or stage 3 fibrosis.	Percent change in FSR from baseline to end of treatment (24 weeks of treatment).
To assess changes in liver stiffness as measured by FibroScan® and by Magnetic Resonance Elastography (MRE).	Observed change in liver stiffness by FibroScan from baseline to 24 weeks of treatment Observed change in liver stiffness by MRE from baseline to 12 weeks and 24 weeks of treatment.
To assess the change from baseline in non-invasive markers of fibrosis: ELF™ test score, PIIINP, Hyaluronic acid, CK18, TIMP-1, YKL-40, Alpha 2 macroglobulin, miRNA, ProC3, ProC6, FGF19, and FGF21.	Observed change in non-invasive biomarkers of fibrosis from baseline to 12 weeks and 24 weeks of treatment.
To assess changes in additional non-invasive tests: fibrosis scores: non alcoholic fatty liver disease (NAFLD) fibrosis score and FIB-4.	Observed change in fibrosis scores from baseline to 12 weeks and 24 weeks of treatment.

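### SAP 3.4.1 does not say which FSR scale the signed-rank p-value uses; run on percent change, the test is tilted against finding a fall

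*SAP*

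**What the plan says.** Both documents define the endpoint as percent change. Protocol 8.1.2 has "To assess the % change in FSR from baseline to end of treatment (24 weeks of treatment" and SAP 2.1 has "Percent change in FSR from baseline to end of treatment (24 weeks of treatment".

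The analysis text is wider than the endpoint. Protocol 8.6.1 states "The change in FSR (absolute and relative) from baseline to end of treatment between the first and second deuterated water loading periods will be assessed" and asks for "Estimated mean, standard error and 95% confidence interval of change in FSR (absolute and relative". SAP 3.4.1 states "Wilcoxon signed-rank test will be used for statistical inference". On the quantities to be judged it says "Summary statistics of change in FSR (observed change and percent change) from baseline in FSR will be reported and evaluated", with 0.05 as the threshold. It reports a p-value from that test but does not say whether it belongs to observed change, percent change or both. Only patients with FSR at both times are included. No log or ratio analysis is planned, and the confidence interval that the protocol asks for is not carried into the SAP's FSR text.

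The status of the test is also mixed. Protocol 8.3 says "Statistical significance will be considered to have been reached at an alpha level of 0.05", whereas SAP 3.1.5 says that no formal hypotheses will be tested. SAP section 6 declares no departures from the protocol analysis.

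**The concern.** The signed-rank test ranks the sizes of the changes and compares the rank total of the rises with that of the falls. It tests for no change only if the changes are symmetric about zero when nothing has happened. Percent change is not symmetric in that sense: it is bounded below at -100% and has no upper bound. A halving is -50% and a doubling is +100%, although they are equal and opposite on a ratio scale. Rises therefore tend to take the larger ranks, and the noisy baseline sits in the denominator.

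The drug is expected to lower FSR. On this scale a true fall is harder to detect, the mean percent change is pulled upward, and chance rises are flagged more often than chance falls. Leaving the scale open also allows it to be chosen after the data are seen.

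**Working it through.** The plan gives no power, effect size or SD for FSR, so there is no stated figure to reproduce.

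**Step 1: symmetry under no effect.** Let x and y be a patient's baseline and Week 24 FSR, and R = y/x. Protocol 6.3 and 6.4.5 describe the same labelling procedure twice: 50 ml three times a day for seven consecutive days, with four samples. (Seven days from Day 155 end on Day 161, but 6.4.5 gives Day 162; that needs reconciling, and I take the periods as intended to match.) With no drug effect and stable disease, x and y are exchangeable, so:
- y - x is symmetric about zero.
- R and 1/R have the same distribution, so log R is symmetric about zero.
- R - 1 is not. Symmetry about zero would need E[R] = 1, and hence E[1/R] = 1. Since E[1/R] >= 1/E[R], with equality only when R is constant, this fails whenever there is within-patient noise.

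This step needs no distributional assumption.

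**Step 2: size.** Inputs:
- From the documents: 20 patients, alpha 0.05. Sidedness is not stated; two-sided is assumed.
- Assumed: lognormal FSR, between-patient CV 40%, independent within-patient CV of 15 to 35% per loading period, and a true fall of 15% (ratio 0.85).
- Test: exact signed-rank with n = 20, rejecting when the smaller rank sum is 52 or less (attained level 0.0484).

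The mean percent change has a closed form. The log ratio has variance 2 ln(1 + CV²), so E[R] = ratio × (1 + CV²).
- No effect, CV 20%: 1 × 1.04 - 1 = +4.0%.
- True 15% fall, CV 20%: 0.85 × 1.04 - 1 = -11.6%.
- True 15% fall, CV 35%: 0.85 × 1.1225 - 1 = -4.6%.

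The other entries come from simulation with at least 20,000 trials per cell; repeat runs agree to about one point of power.

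| CV | Log-ratio SD | No effect: false rise / fall on percent change | Power, percent change | Power, observed change | Power, log ratio | Mean percent change, true -15% | Median percent change, true -15% |
|---|---|---|---|---|---|---|---|
| 15% | 0.21 | 3.5 / 1.7% | 84% | 87% | 89% | -13.1% | -14.9% |
| 20% | 0.28 | 4.0 / 1.4% | 56% | 64% | 67% | -11.6% | -14.7% |
| 25% | 0.35 | 4.8 / 1.3% | 36% | 46% | 49% | -9.7% | -14.6% |
| 35% | 0.48 | 5.6 / 1.0% | 16% | 27% | 28% | -4.6% | -14.2% |

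The log ratio gives about 2.4 / 2.4% under no effect, and observed change is similarly balanced. On percent change, false rises outnumber false falls by about 2:1 at CV 15% and by somewhat over 5:1 at CV 35%.

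**Step 3: sensitivity.**
- Error shape, CV 20%, true 15% fall: percent change versus log ratio is 54% versus 65% with gamma errors, and 52% versus 63% with truncated normal errors.
- Larger effect, true 20% fall: 100% versus 100% at log-ratio SD 0.15, 92% versus 96% at 0.25, 62% versus 75% at 0.35.
- Fewer pairs, 16 complete, true 20% fall, SD 0.35: 50% versus 62%.

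**The case against.** A reader might infer that the SAP tests FSR only as percent change, so that a true fall will certainly be understated. The documents do not support this.

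- Protocol 8.6.1 and SAP 3.4.1 both also analyse observed change. In the model above it has no tilt under no effect and is within about 1 to 3 points of the log ratio in power. This stands: the harm arises only if the p-value is run on percent change. Observed change is not a general safeguard, however. If the proportional change varies independently of measured baseline, its power for a 20% fall at log-ratio SD 0.35 is 61%, against 75% for the log ratio.
- SAP 3.1.4 reports the median beside the mean, and the median percent change is nearly unbiased. This stands: understatement applies to the mean and the test, not to every planned summary.
- The documents give no FSR variability or distribution, so the size of the loss is conditional. This stands. If percent change were itself symmetric, the planned test would be valid and the log ratio would be the skewed scale, towards falls (4.7% false falls against 1.3% false rises at an SD of 35 points). That situation is incompatible with exchangeable periods under no effect, so it does not remove the tilt shown in step 1. It would matter if untreated FSR drifted or the two labelling periods differed.
- FSR is secondary, the 20 patients were chosen on clinical assessment for safety, and SAP 3.1.5 disclaims formal testing. The overall false-positive rate barely moves: at CV 20%, 4.0 + 1.4 = 5.4% against about 4.8%. The error is also conservative for claiming a fall. This lowers the severity, but a p-value judged at 0.05 is still planned.

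**Conclusion.** The point holds conditionally. The scale of the FSR p-value is unspecified, and on the scale that defines the endpoint the signed-rank test is tilted against a fall. The direction follows from exchangeability of the two labelling periods under no effect. The size rests on lognormal error and an assumed within-patient CV. At CV 15, 20, 25 and 35%, percent change gives up about 5, 11, 13 and 12 points of power against the log ratio for a true 15% fall. At CV 20% the mean would show about -11.6%, while the median would show about -14.7%. With low variability or a large effect the loss is negligible. Severity is low; this is a cheap improvement to a supportive analysis.

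**What to change.** In SAP 3.4.1:
- Name the scale of the p-value, and apply the signed-rank test to log(Week 24 FSR / baseline FSR).
- Report the back-transformed Hodges-Lehmann estimate, or the geometric mean ratio minus 1, as the percent change with a 95% CI. This keeps the endpoint in percent terms and supplies an interval, which the SAP's FSR text lacks.
- Keep the protocol's raw absolute and percent change summaries (mean, SE, 95% CI, median) as descriptive tables. They should not be reduced to listings, because Protocol 8.1.2 and 8.6.1 call for them.
- Record the change in SAP section 6, and align SAP 3.1.5 with the test that is actually planned.

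The cost is one derived variable and a documented departure from the protocol's raw-scale inference. No new data are needed.
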